In summary, many hearing-impaired patients function with noticeable hearing asymmetry. When hearing is asymmetric and the loss in the poor ear is moderate-to-profound, lack of treatment for that ear is very common, which results in monaural hearing. Listening with just one ear, particularly a hearing-impaired ear, is detrimental to signal segregation and communication. Individuals with asymmetric hearing loss frequently seek medical care due to pervasive communication difficulties. The only available treatment that can provide hearing to the deaf ear is a CI. At this time, individuals with asymmetric hearing loss are not routinely implanted in the poor hearing ear simply because the contralateral, better hearing ear has hearing loss in the moderate range rather than the severe to profound range. A prospective, single-arm, multi-center clinical trial is critically needed to address the deficits of patients with asymmetric hearing loss and explore potential treatment with a CI. Outcomes from this study will also inform a future pivotal clinical trial.

Study Objectives

Primary Objective: Obtain preliminary efficacy data in adults with asymmetric hearing loss who receive a cochlear implant (CI) in the poor hearing ear and maintain a hearing aid (HA) in the better hearing ear. Efficacy is defined as post-implant improvement in the poor ear with a CI compared to pre-implant with a HA. Measures are sound field threshold levels and CNC monosyllabic words in quiet.

Secondary Objectives:

1. Obtain efficacy data related to bimodal hearing. Efficacy is defined as post-implant improvement (CI in poor ear + HA in better ear) compared to the pre-implant best-aided condition (either HAs in both ears, or a HA in the better ear alone for adults with no aidable hearing in the poor ear). Measures are sound localization, speech recognition in noise, speech recognition at soft presentation levels, perceived hearing handicap, and reported quality of life.
2. Evaluate safety associated with cochlear implantation in individuals with asymmetric hearing loss. The safety evaluation will be based on the number, type and degree of all adverse events.
3. Collect essential preliminary information related to test measures and methodology that can be used clinically in a future Phase III clinical trial (e.g., localization, listening in noise, listening at soft levels).

Study Design

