The Participant Interview Form will be completed by the investigator after questioning the participant. This will provide information regarding tinnitus, dizziness, medications, the incision/implant site, and other relevant information.

Participants' take-home speech processor programs

The audiologist at each center will provide a de-identified copy of the speech processor programs. This will document relevant information regarding the parameters used by the participant with their speech processor.

Aural Rehabilitation

All participants will be encouraged by their audiologist to practice daily for 15-30 minutes listening with their CI only for at least the first 6 weeks of implant use and then 3 times a week for an additional 6 weeks. During practice, participants can listen with their CI through direct audio input to their CI or can listen through the CI alone by plugging the better hearing ear with an earplug. Each participant will be given a list of practice materials available for use on a computer, tablet, smart phone or through a CD player.

Post-Implant Study Testing (3, 6, 9 and 12 months after Initial Stimulation)

The duration of each session will be approximately 4-5 hours and will be completed in 1-2 visits. Audiometric, speech recognition, localization, self-assessment, speech processor program, and adverse event data will be obtained at each of the four post-implant test intervals. Post-implant test intervals should occur within a \pm 30 day window around the target test date. Speech recognition and localization data will be obtained in multiple listening conditions as listed below.

Unaided Audiometric Threshold Levels*

Air conduction thresholds using insert earphones will be obtained for each ear at 250, 500, 1000, 2000, 3000, 4000, 6000 and 8000 Hz. Masking will be used when appropriate

*If unaided audiometric testing at the initial stimulation reveals no response at each frequency in the CI ear, unaided audiometric testing in the CI ear does not need to be done at each post-implant test session.

Hearing Aid in the Better Ear

Verification of Hearing Aid

Each hearing aid will be checked for proper function and sound quality (e.g., listening check, electroacoustic analysis, patient report).

Aided, FM Tone Sound Field Threshold Levels

Aided FM tone sound field levels will be obtained at 250, 500, 1000, 2000, 3000, 4000 and 6000 Hz.

CNC Word Test

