A record of all adverse events will be kept. No formal statistical hypothesis will be tested. The primary safety endpoint will be 6 months post-implant. Adverse event information through 6 months post-implant will be summarized by event type, severity/seriousness, and whether related to the device and/or implant procedure.

Efficacy

The primary study objective is to obtain preliminary efficacy data in adults with asymmetric hearing loss who receive a CI in the poor hearing ear and maintain a HA in the better hearing ear. Efficacy is defined as post-implant improvement in the poor ear with a CI compared to pre-implant with a HA. Measures are sound field threshold levels and CNC monosyllabic words in quiet.

A secondary objective is to obtain efficacy data related to bimodal hearing. Efficacy is defined as post-implant improvement (CI in poor ear + HA in better ear) compared to the pre-implant best-aided condition (either HAs in both ears, or a HA in the better ear alone for adults with no aidable hearing in the poor ear). Measures are sound localization, speech recognition in noise, speech recognition at soft presentation levels, perceived hearing handicap, and reported quality of life.

Sample Size Justification

The primary efficacy endpoint is change in CNC performance from pre-implant to post-implant, with most of the gain expected to be achieved by 6 months. A clinically meaningful change on the CNC test is .10. In our past research we have found CNC standard deviations that range from .06 to .24. Assuming a correlation between repeated measures of .5 (typical in our work) these values translate into standardized mean differences (Cohen's *d*) ranging from .42 to 1.67. At the minimum effect size, a sample size of 37 is necessary for power of .80, the common standard (Cohen and Cohen, 1983; Keppel, 1991; Cohen, 1992). As indicated, the planned sample size will provide adequate to excellent power to detect clinically meaningful differences. Up to 40 participants will be enrolled to allow for attrition.

Note that the analyses described later will often be more complex than the simple approach used here for power calculations (a dependent means t-test), often involving change over longer periods of time, examining nonlinearity in the change profiles, and including additional predictors (e.g., patient characteristics). The impact of these modifications will generally be to increase power by including additional measures that

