A UADE is "any serious adverse effect on health or safety or any life-threatening problem or death caused by, or associated with, a device, if that effect, problem, or death was not previously identified in nature, severity, or degree of incidence in the investigational plan or application (including a supplementary plan or application), or any other unanticipated serious problem associated with a device that relates to the rights, safety, or welfare of subjects." [FDA 21 CFR 812.3(s)]

Investigator Responsibilities

Throughout the course of the study, all efforts will be made to remain alert to possible AEs. Of primary concern will be the participant's safety and providing appropriate medical care. Detailed information regarding AEs will be recorded by the study site at

the time an AE occurs using the “*Adverse Event CRF*”. All AEs will be recorded from the day of enrollment to the time when the participant exits the study or to study termination, whichever is the last, even if the event was acknowledged as a risk factor in the Informed Consent.

AEs will be recorded on the “*Adverse Event CRF*” and will include the following information:

- Date of onset
- Date reported to the clinic
- Description of the AE
- Seriousness (yes or no)
- Investigator’s assessment of the relationship of the AE to the device
- Investigator’s assessment of the relationship of the AE to the procedure
- Treatment
- Outcome
- Relationship to device, implantation procedure and/or underlying disease

A UADE will be reported directly to the study site’s IRB and the Sponsor within 10 working days of learning of the event or as dictated by the study site’s IRB, whichever is sooner. Information regarding the UADE will be recorded on the “*Unanticipated Adverse Device Effect CRF*”.

Adverse Event Follow-up – Investigator Responsibilities

All AEs must be followed until resolution. The study site will follow-up as necessary with the participant to explain as well as possible the reason for and nature of the AE. This may include additional tests or consultation with other health care professionals. The Sponsor may request that the study site perform additional specific evaluations. AE follow-up information, as needed, will be recorded using a “*Previously Reported AE or UADE Follow-Up CRF*”.

Adverse Event Follow-up – Sponsor Responsibilities

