All AEs will be reported annually to FDA in accordance with the IDE regulation [FDA 21 CFR Part 812.150(b)(5)]. All UADEs will be reported to FDA within 10 calendar days of the event in accordance with FDA 21 CFR Part 812.46(b) and 812.150(b)(1). The Sponsor will notify all study sites of new safety information that alters the current risk-benefit assessment or that would be sufficient to consider changes in the overall conduct of the clinical trial.

Protocol Deviations

Any study-related activity not in compliance with the approved protocol is considered to be a protocol deviation. Deviations required to protect the life or welfare of a participant do not require approval and should be performed immediately. The IRB must be notified within 5 days of the event.

If a study participant is unable to return for a study visit within the allotted \pm 30 day window around the target visit, or if a study visit is incomplete or otherwise completed incorrectly, these events will be tracked and logged. The Primary Investigator at each site will monitor this log and continually assess the nature and degree of these deviations to determine the impact of these events on safety or performance of the participant or data integrity.

Study Completion

Completed Participants

Participants are considered completed when all assessments through 12 months post-implant have been completed as mandated by the study protocol. Only participant data obtained with the originally implanted device will count toward the primary endpoint.

Discontinued Participants

Any participant can discontinue the study at any time without prejudice. The site's Primary Investigator may also discontinue a participant at any time if health is a risk or if the participant is uncooperative and otherwise impacting the integrity of the data. All withdrawals will be documented including the reason for withdrawal. Efforts will be put forth to ensure near complete follow-up, particularly on assessment of primary outcomes and occurrence of adverse events. Regular reminders, flexibility in scheduling of study visits to coincide with clinical visits, and close monitoring of due dates will facilitate obtaining as complete data as possible. Participants lost to follow-up will be contacted at least three times by phone, email or mail.

Premature Study Termination

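### A site that meets its own UADE reporting limit can leave the Sponsor past its stated FDA limit, and the only described AE summary stops at 6 months although AEs are recorded to study exit or later

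*Combined protocol and SAP*

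**What the plan says.** **UADE reporting.** Under Investigator Responsibilities, a site reports a UADE to its IRB and to the Sponsor "within 10 working days of learning of the event or as dictated by the study site’s IRB, whichever is sooner". Under Adverse Event Follow-up – Sponsor Responsibilities, the commitment is: "All UADEs will be reported to FDA within 10 calendar days of the event". That sentence cites two FDA regulations on which it relies, but their text is not in the document.

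**Scope of AE collection.** Study Objectives and the Safety section both say: "The safety evaluation will be based on the number, type and degree of all adverse events". Post-Implant Study Testing says that "adverse event data will be obtained at each of the four post-implant test intervals", with visits allowed a plus or minus "30 day window around the target test date". Investigator Responsibilities adds: "All AEs will be recorded from the day of enrollment to the time when the participant exits the study". The same sentence extends recording to study termination if that comes later. Completed Participants puts completion at 12 months.

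**AE summary.** The Safety section says: "The primary safety endpoint will be 6 months post-implant". It continues: "Adverse event information through 6 months post-implant will be summarized by event type, severity/seriousness, and whether related to the device and/or implant procedure". It plans no hypothesis test. Data Analysis describes no analysis of adverse events.

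**The concern.** The two UADE sentences bind different parties, but they form a chain: for an event at another center, the Sponsor depends on the site's report. The site's limit is in working days and starts when the site learns of the event. The Sponsor's is in calendar days and starts at the event itself. The later link therefore has the shorter unit and a start that is the same or earlier. If the site uses its allowance, the Sponsor's stated deadline passes without anyone breaking the site rule. What is at stake is timely reporting of the most serious class of event.

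The second issue is completeness. The objective covers all adverse events and the data will be held, yet the only summary with described content covers the first part of follow-up. The study is meant to inform a Phase III trial. Its Risk Benefit Statement also names a possible added risk in this population, sound interference between implant and hearing aid, to be monitored. A safety report narrower than the stated objective would serve both purposes less well.

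**Working it through.** **1. UADE clocks**

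Inputs: Sponsor limit of 10 calendar days from the event (Sponsor Responsibilities); site limit of 10 working days from learning of it (Investigator Responsibilities). Working days are taken as Monday to Friday.

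Let W be the calendar length of 10 working days and d the days from the event to the site's learning of it. If the site reports on its last permitted day:

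days past the Sponsor's limit = d + W − 10.

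| Day the site learns | W, next day counted as day 1 | W, first working day may be the day of learning |
|---|---|---|
| Monday | 14 | 11 |
| Tuesday to Friday | 14 | 13 |
| Saturday | 13 | 13 |
| Sunday | 12 | 12 |

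- Same-day learning (d = 0), no holiday: from 11 − 10 = 1 to 14 − 10 = 4 days late.
- One public holiday, next-day count: W can reach 17, so up to 17 − 10 = 7 days late.
- Late learning, with d = 7 as an assumed value and no holiday: from 7 + 11 − 10 = 8 to 7 + 14 − 10 = 11 days late.
- If d exceeds 10, the Sponsor's limit has passed before the site's clock starts, whatever the site's limit is.

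A gap between event and learning is foreseeable. The Adverse Event CRF has separate fields for the onset date and the date the clinic was told, and study visits are three months apart.

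**2. AE summary**

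Inputs: post-implant visits at 3, 6, 9 and 12 months after initial stimulation (Study Design); stimulation 2 to 4 weeks after surgery (Initial Stimulation of the Cochlear Implant); summary through 6 months (Safety).

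- Intervals after the cut: 9 and 12 months, so 2 of 4.
- Share of time from stimulation to the 12-month visit: (12 − 6)/12 = 50%.
- Share counted from surgery, with a month of 30.44 days: 2 weeks is 0.46 months, giving 6/12.46 = 48%; 4 weeks is 0.92 months, giving 6/12.92 = 46%.
- If the cut and the end are the actual visits, each up to 30 days early or late, and 6 and 12 months are 182.6 and 365.25 days, the share from surgery runs from (335.25 − 212.6)/(28 + 335.25) = 34% to (395.25 − 152.6)/(14 + 395.25) = 59%.

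These are shares of time, not of events. They end at the 12-month visit, so they are not bounds on the AE recording period, which can run to study termination.

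**The case against.** **On the UADE limits.** Lateness is not inevitable. It requires a site to use nearly all its allowance or to learn late, with no IRB rule short enough to prevent it. An IRB limit of 5 working days would be 5 to 7 calendar days on the next-day count without a holiday, which leaves the Sponsor time if learning is same-day. This stands, and it is why the finding says *can*. It is no cure: the protocol gives no IRB figure, and no IRB limit on the site removes the difference in start points. With a Monday holiday after learning on a Friday, even 5 working days end on calendar day 10.

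It can also be said that the Sponsor's sentence defers to regulations, so its clock may run differently in practice. That cannot be checked from the document. A reader might infer that the plan breaches those regulations, or that one of the two limits is the correct one; the document supports neither reading.

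**On the AE summary.** Six months is labelled the primary safety timepoint and may be deliberate. A reader might infer that later events are lost or go unreviewed. They are not: all AEs go to FDA annually, the DSMB reviews cumulative data, and Study Report and Publication promises analysis of the compiled data at completion. What remains is that none of these describes an AE summary beyond 6 months.

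**Two further readings that do not hold as findings.** One is that the 6-month cut has an uncertain start. Study Design and the Post-Implant Study Testing heading time post-implant visits from initial stimulation, and the alternative differs by only 2 to 4 weeks. The other is that the AE and SAE definitions, which speak of unexpected occurrences (and, for AEs, of onset after implantation), exclude expected or earlier events. Investigator Responsibilities gives an explicit rule: record from enrollment, including risks listed in the consent. At most, both call for optional wording clarification.

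**Conclusion.** The UADE point holds on the text. At their outer limits the two sentences cannot both be met for an event that the Sponsor learns of through the site. With same-day learning and no holiday, the Sponsor is about 1 to 4 days past its stated limit, more with a holiday, and one day more for each day of delay in learning. This rests on a literal reading of the Sponsor's start point, on Monday-to-Friday working days, and on no shorter IRB limit applying. It is an internal inconsistency that needs correcting.

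The AE summary point holds in a smaller form. The only described summary leaves out 2 of 4 post-implant intervals, roughly half of follow-up to the 12-month visit, while the objective covers all adverse events. It is a completeness gap in a descriptive secondary objective. No event is shown to be lost and no inference changes.

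**What to change.** 1. Reconcile the UADE sentences in Investigator Responsibilities and Sponsor Responsibilities so that the site's limit ends before the Sponsor's and the Sponsor's clock starts at a point it can know. The Sponsor should settle the actual limits against the regulations it cites. The cost is a wording change and notice to the sites.

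2. Keep 6 months as the primary safety timepoint. Add to the Safety section a descriptive AE table in the same layout through the end of AE recording, that is, study exit or termination, whichever is later. The cost is one more table from data already collected. Its AE count may be higher than the 6-month count, and cannot be lower.
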